6.2.3 Follow Up Period and Trial Completion

For all patients completing the study according to the protocol without persisting AE at Visit 15/EOT, a follow-up visit (Visit 16) can be performed as a phone visit by the investigator at the end of the follow-up period of 7 days. Visit 16 should occur 7 days after Visit 15/EOT within the timeframe (+7 days).

During the follow-up period, results of a SMBG test reveal blood glucose of >240 mg/dL (13.3 mmol/L) after an overnight fast the patient should contact the site, and the investigator should follow procedure described in the Sections 4.2.1 and 3.3.4.1.

The following should be confirmed and recorded at Visit 16 via telephone:

- · Concomitant therapies
- · Any AEs
- · SMBG result

Patients completing the study according to the protocol with persisting AE at Visit 15/EOT and patients who prematurely discontinue the study, the patient should return to follow up visit (Visit 16, 7 days after Visit 15/EOT). The following examinations should be performed at Visit 16 in addition to the above mentioned items:

- · Physical examination
- · Vital signs
- · Collection of blood (include FPG sample) and urine samples for safety laboratory evaluation.

7. STATISTICAL METHODS AND DETERMINATION OF SAMPLE SIZE

7.1 STATISTICAL DESIGN - MODEL

This is a 52-week, randomised, multi-centre, parallel group study to investigate the safety and efficacy of empagliflozin (10 mg or 25 mg administered orally once daily) as add-on therapy to GLP-1 RA (i.e., liraglutide) in patients with T2DM with insufficient glycaemic control.

Patients to be enrolled in this study are those with T2DM who have insufficient glycaemic control despite background monotherapy with liraglutide. Empagliflozin 10 mg or 25 mg is administrated with liraglutide over 52 weeks. Patients will be randomly assigned to empagliflozin 10 mg or 25 mg.

The primary endpoint in this trial is frequency of patients with drug-related adverse events (AE) during 52 weeks of treatment. The secondary endpoint in this study is the change from baseline in HbA1c after 52 weeks of treatment.

Based upon these design considerations, the trial will be analysed using descriptive statistics for the primary endpoint. For the secondary endpoint, the HbA1c changes from baseline is considered as normally distributed based on experiences with similar endpoints in other trials and literature data. Therefore, the statistical model used for the secondary endpoint is a restricted maximum likelihood (REML)-based mixed model with repeated measures (MMRM) including the fixed effects treatment, baseline renal function, prior use of antidiabetic agents, visit, treatment-by-visit interaction and the covariate baseline HbA1c, baseline HbA1c-by-visit interaction.

7.2 NULL AND ALTERNATIVE HYPOTHESES

There will be no confirmatory statistical testing in this study.

7.3 PLANNED ANALYSES

No confirmatory statistical analysis is planned. The statistical analysis will be based on the following populations. With regard to each efficacy and safety endpoint during the randomised 52-week treatment period, the term "baseline" refers to the last observed measurement prior to the administration of any randomised trial medication.

Treated set

The treated set (TS) will consist of all patients who were randomised and treated with at least one dose of the study drug. The assignment of patients to treatment group will be based on the first study drug intake in the double-blind treatment period.

Full analysis set

Page 59 of 73

Proprietary confidential information © 2017 Boehringer Ingelheim International GmbH or one or more of its affiliated companies

The full analysis set (FAS) will consist of all patients in TS who were treated with at least one dose of the randomised study drug and had a baseline HbA1c assessment. The assignment of patients to treatment groups will be based on the randomised study drug at time of randomisation.

7.3.1 Primary endpoint analyses

The primary endpoint in this trial is frequency of patients with drug-related adverse events (AE) during 52 weeks of treatment, which will be analysed in the same way as other safety analysis. More details are given in Section 7.3.4.

7.3.2 Secondary endpoint analyses

HbA1c

The change from baseline in HbA1c after 52 weeks of treatment will be calculated on FAS by treatment using MMRM. The statistical model is as follows:

HbA1c change from baseline = overall mean + treatment + baseline HbA1c + baseline renal function + prior use of antidiabetic agents + visit + treatment-by-visit + baseline HbA1c-by-visit + error

Analyses will include "treatment", "baseline renal function", "prior use of antidiabetic agents", "visit" and "treatment-by-visit" interaction as fixed effects, "baseline HbA1c", and "baseline HbA1c-by-visit" interaction as covariates. The term "baseline HbA1c" refers to the last HbA1c assessment prior to the administration of any randomised medication (HbA1c values at Visit 7) and not to the HbA1c measurement used for the stratification in the randomisation. "Baseline renal function" will be a classification effect derived from the categorisation of eGFR at baseline. Regarding "prior use of antidiabetic agents", patients will be classified as liraglutide only, OAD only or liraglutide plus OAD. An unstructured covariance structure will be used to model the within-patient measurements. If the analysis fails to converge, the following covariance structure will be tested: compound symmetry, variance components and Toeplitz. The covariance structure converging to the best fit, as determined by Akaike's information criterion, will be used. The Kenward-Roger approximation will be used to estimate the denominator degrees of freedom. This model will also be used to evaluate the change from baseline in HbA1c overtime during the 52-week treatment period.

Only the available data which were observed whilst patients were on treatment will be included in the analysis. Missing data are handled implicitly by the above statistical model, rather than by using any imputation. This approach will also additionally set to missing all values measured after the restricted antidiabetic medication during the trial (See Section 4.2.2)

The last available on-treatment HbA1c value is defined as the last available HbA1c value measured up to a period of seven days after the last dose of the randomised study medication or the last available HbA1c value prior to the restricted antidiabetic medication during the trial (See Section 4.2.2).

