7.7 DETERMINATION OF SAMPLE SIZE

The draft version of Japanese guideline 'Clinical Evaluation Guidelines for Antihyperglycemic Drugs' [R15-2907] requires one year long-term study on background therapies with several approved antidiabetic drugs. The guideline requires observing 50 to 100 patients during one year for each background therapy. The sample size for this trial was determined according to the outcome of the PMDA consultation on December 2014. At least 50 patients as 52-week completers including two doses were necessary for the background therapy with GLP-1 RA for safety evaluation.

Based on the above, and allowing for a discontinuation/dropout rate of approximately 20% during the trial, the sample size for empagliflozin 10 mg and 25 mg were determined at 32 per arm in the GLP-1 RA background group.

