### **3. INTRODUCTION**

As per ICH E9, the purpose of this document is to provide a more technical and detailed elaboration of the principal features of the analysis described in the protocol, and to include detailed procedures for executing the statistical analysis of the primary and secondary variables and other data.

This TSAP assumes familiarity with the Clinical Trial Protocol (CTP), including Protocol Amendments. In particular, the TSAP is based on the planned analysis specification as written in CTP Section 7 “Statistical Methods and Determination of Sample Size”. Therefore, TSAP readers may consult the CTP for more background information on the study, e.g., on study objectives, study design and population, treatments, definition of measurements and variables, planning of sample size, randomization.”

SAS® Version 9.4 will be used for all analyses.

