## **6.7 BASELINE, TIME WINDOWS AND CALCULATED VISITS**

With regard to efficacy and safety endpoints, the term “baseline” refers to the last observed measurement prior to administration of any randomised study medication.

Measurements taken prior to the first intake of randomised study medication will be considered pre-treatment values. These pre-treatment values will be assigned to a visit according to the nominal visit number as record on the eCRF or provided by the laboratory.

The date and clock time of the first drug administration will be used to separate pre-treatment from on-treatment values. Measurements taken after the first intake of randomised study drug will be considered on-treatment values if they have been obtained up to end of the parameter specific follow-up period as defined in [Table 6.7: 1](#) below and will be assigned to the randomised study drug for efficacy analyses and to the first study drug taken for safety analyses.

Measurements taken after the end of the endpoint specific follow-up period and after the last intake of study drug will be considered post-treatment values.

**Table 6.7: 1** Endpoint specific follow-up period for the assignment to active treatment

Endpoint	Last day of assignment to treatment phase (days after study drug stop date)
Efficacy	
HbA1c	7
FPG	1
Body weight	1
Blood pressure	1
Insulin and glucagon	1
Waist circumference	7
Safety	
Adverse events	7
Safety laboratory measurements	3
Pulse rate	1

On-treatment efficacy and safety measurements will be assigned to visits based on time windows around the planned visit dates. These time windows are defined based on the planned number of days after the date of first administration of study drug (usually this is at Visit 7).

The midpoint between two on-treatment visits defines the end of a time window, with the midpoint being included in the time window of the preceding visit. The end of the time window of the last on-treatment visit is endpoint dependent (see [Table 6.7: 1](#)).

**Table 6.7: 2** Time windows for on-treatment HbA1c, body weight, and waist circumference measurements scheduled for each on-treatment visit

Visit number	Visit label	Planned days	Time window (actual days on treatment)	
			Start	End A
7	Baseline	0	NA	1 B
9	Week 8	56	2	98
11	Week 20	140	99	196
13	Week 36	252	197	308
15	Week 52/EoT	364	309	Study drug stop date + X days

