### **7.5.2 Secondary endpoint**

#### Mixed model repeated measures (MMRM)

Restricted maximum likelihood-based MMRM will be performed on FAS (OC) with the following model.

HbA1c change from baseline

= overall mean + treatment + baseline HbA1c + baseline renal function + visit + treatment-by-visit interaction + baseline HbA1c-by-visit interaction + error

In the above MMRM model, “treatment”, “baseline renal function”, “visit” and “treatment-by-visit” interaction are fixed classification effects, “baseline HbA1c” and “baseline HbA1c-by-visit” interaction are covariates.

The term “baseline HbA1c” refers to the last HbA1c assessment prior to the administration of any randomised medication (HbA1c values at Visit 7) and not to the HbA1c measurement used for the stratification in the randomisation.

“Baseline renal function” is a classification variable derived from the categorization of eGFR at baseline as specified in [Section 5.4.1](#) and [Table 6.4: 1](#). For modeling purpose, eGFR categories  $<90$  and  $\geq 90$  are used in the model.

Unstructured covariance structure will be used to model the within-patient correlation due to repeated measurements. If the model fails to converge, the following covariance structure

will be tested: compound symmetry, variance components and Toeplitz. The covariance structure, with which the model converges and provides the best fit as determined by Akaike information criterion (AIC), will be used for final analysis. The Kenward-Roger approximation will be used to estimate the denominator degrees of freedom.

Because the change in HbA1c from baseline at each on-treatment visit is used as the outcome variable in the MMRM model, the above model is also used to evaluate the HbA1c change from baseline overtime.

Only the available data which are observed whilst patients are on treatment will be included in the analysis. Missing data are handled implicitly by the above statistical model, rather than by using any imputation. This approach will also additionally set to missing all values measured after the use of restricted antidiabetic medication during the trial (see Section 4.2.2 in CTP).

[REDACTED]

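### If the unstructured HbA1c model does not converge, every fallback covariance assumes equal variance at all visits, so the Week 52 standard error is wrong when spread differs by visit (low priority)

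*Protocol*

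**What the plan says.** The main choice is sound. Protocol 7.3.2 states: "An unstructured covariance structure will be used to model the within-patient measurements". This gives each visit its own variance.

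The point concerns the next step. On non-convergence the protocol continues: "the following covariance structure will be tested: compound symmetry, variance components and Toeplitz". The selection rule is: "The covariance structure converging to the best fit, as determined by Akaike's information criterion, will be used". On inference it adds: "The Kenward-Roger approximation will be used to estimate the denominator degrees of freedom". SAP 7.5.2 repeats the list unchanged ("will be tested: compound symmetry, variance components and Toeplitz"), with the same AIC rule and the same degrees of freedom. SAP section 3 names SAS as the software ("Version 9.4 will be used for all analyses").

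The visible text of neither section lists a heterogeneous structure, a variance grouped by visit, or a robust standard error.

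**The concern.** A fallback covariance should be simpler than the unstructured one without giving up what the Week 52 result depends on. This list keeps some within-patient correlation (Toeplitz, compound symmetry) or none (variance components), but every member puts a single variance on the diagonal. Structures in between, simpler than unstructured but with a separate variance per visit, are skipped.

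Neither safeguard in the text helps. AIC can only rank the candidates it is given, and all of these share the restriction. Kenward-Roger adjusts for small samples on the footing that the chosen structure is right; it does not correct a wrong variance pattern.

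At stake is the precision reported for the only secondary endpoint. Both arms are active, so the per-arm change carries the efficacy description, and the dose difference comes from the same model.

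**Working it through.** **Inputs from the documents**
- On-treatment HbA1c visits: Weeks 8, 20, 36 and 52 (SAP 6.7, table titled "Time windows for on-treatment HbA1c, body weight, and waist circumference measurements scheduled for each on-treatment visit").
- Sample size, protocol 7.7: "At least 50 patients as 52-week completers including two doses were necessary", with about 20% dropout. Check: 50 / 0.80 = 62.5, rounded up to 63, hence 32 per arm and 64 in total; 64 × 0.80 = 51.2 completers. The plan's figure is reproduced.

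**Assumptions (not in the documents)**
- SD of HbA1c change by visit, within-patient correlation, and a two-sided 95% interval.
- Variance components is read in its usual residual form, not grouped by visit.

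**Covariance parameters with four visits**
- Unstructured: 4 × 5 / 2 = 10.
- Planned fallbacks: Toeplitz 4, compound symmetry 2, variance components 1.
- Skipped: heterogeneous Toeplitz 4 + 3 = 7; heterogeneous AR(1) or compound symmetry 4 + 1 = 5.

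**Step 1: complete data, by hand.** An equal-variance fit estimates roughly the mean of the visit variances, so model SE / true SE at Week 52 ≈ sqrt(mean of SD²) / SD at Week 52.
- SD 0.5, 0.6, 0.7, 0.8: mean variance = (0.25 + 0.36 + 0.49 + 0.64) / 4 = 0.435; square root 0.66; 0.66 / 0.8 = 0.82. Coverage = 2Φ(1.96 × 0.82) − 1 ≈ 89%.
- Same values reversed, so that spread falls to 0.5: 0.66 / 0.5 = 1.32. The standard error is 32% too large and coverage about 99%.
- Constant SD: ratio 1.

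**Step 2: large-sample fit with 20% dropout.** SD rises linearly in weeks; the ranges cover all three fallbacks and several correlation patterns.

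| Week 52 SD / Week 8 SD | Model SE / true SE | Coverage of nominal 95% |
|---|---|---|
| 1.25 | 0.88-0.90 | 91-92% |
| 1.5 | 0.81-0.83 | 89-90% |
| 2.0 | 0.73-0.76 | 85-86% |

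At ratio 1.0 there is no material loss (0.98-1.01).

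**Step 3: REML simulation at the planned size.** 64 patients, 20% dropout, the SAP's type of mean model, 250 runs per scenario, approximate fixed degrees of freedom in place of Kenward-Roger. Entries are model SE / empirical SD of the Week 52 dose difference, then coverage.

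| Structure | SD ratio 1.0 | SD ratio 1.5 | SD ratio 2.0 |
|---|---|---|---|
| Unstructured | 0.99, 94.4% | 1.01, 95.2% | 0.96, 94.8% |
| Compound symmetry | 0.98, 94.4% | 0.82, 89.6% | 0.71, 85.6% |
| Variance components | 0.97, 94.4% | 0.84, 89.6% | 0.73, 87.6% |
| Toeplitz | 0.99, 95.2% | 0.84, 90.0% | 0.74, 87.6% |
| Heterogeneous compound symmetry | 1.01, 94.4% | 1.02, 95.6% | 0.97, 94.8% |

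Among the three planned fallbacks AIC chose Toeplitz in every run, so selection did not remove the problem. Monte Carlo error at 90% coverage is sqrt(0.9 × 0.1 / 250) ≈ 1.9 percentage points.

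**Step 4: a second simulation** (32 per arm, correlation 0.8 per visit step, 20% dropout, 300-400 runs).
- SD 0.5 to 0.8 (ratio 1.6): fallback SE 14-16% too small; coverage 91-93% for an arm mean and 89-90% for the dose difference.
- SD 0.45 to 0.9 (ratio 2.0): SE 27-29% too small; coverage 83-86%.
- Heterogeneous Toeplitz: about 95-96% (arm mean) and 93-95% (dose difference).

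**Step 5: how often the fallback would be reached.** Unstructured REML was fitted to 1,080 simulated trials (64 patients, four visits, 20% or 40% dropout, correlation 0.6 to 0.95, flat or rising SD). It failed in none; the upper 95% bound is about 3 / 1,080 = 0.3%. The optimiser was not SAS and dropout was monotone, so this is indicative only.

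**The case against.** The strongest reply is that the fallback will almost certainly not be used. Ten covariance parameters are few for about 64 patients, and unstructured held 94-95% coverage in Step 3. That stands, and it sets the priority.

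It follows that the coverage losses above are not those of the planned procedure. The equal-variance structures were fitted to every simulated dataset, not only to those where unstructured failed. This also stands. Nor has it been shown that a heterogeneous structure would converge where unstructured does not, so the order still needs a last resort.

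Rising spread is an assumption. A reader might infer that Week 52 is the most variable visit as a matter of course, but the documents give no SDs by visit. Some features of the plan may restrain growth in spread: baseline HbA1c-by-visit is in the model, values after restricted antidiabetic medication are set to missing, and patients with confirmed high fasting glucose are withdrawn (protocol 3.3.4.1).

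The consequence is limited too. Protocol 7.2 rules out confirmatory testing, the primary endpoint is drug-related adverse events, and the visible text gives neither a confidence level nor an interval for Week 52. SDs in the summary tables (SAP section 7) could reveal unequal spread. Protocol 7.5 mentions ANCOVA with LOCF; a Week 52 ANCOVA, if run, would not pool variance over visits. SAP 7.5.2 ends in a redacted block, so one cannot conclude that no sensitivity analysis exists.

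None of this makes the written rule correct in the one situation it is meant for.

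**Conclusion.** The point holds as a low-priority improvement. If unstructured does not converge, the rule allows only equal-variance structures, and the Week 52 standard error is then generally wrong when the variance of HbA1c change differs by visit. For an SD that rises 1.5- to 2-fold it is about 15-29% too small, with coverage of roughly 83-93%; for a falling SD it is too large; for a constant SD there is no material loss. The size rests on assumed SDs, assumed correlations and an assumed 95% level.

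A reader might infer that the planned Week 52 HbA1c result is itself too precise. The documents do not support that: the planned analysis is unstructured, which kept close to nominal coverage in every scenario of Step 3. No type I error claim is affected, since there is no formal test.

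**What to change.** In protocol 7.3.2 and SAP 7.5.2, put heterogeneous-variance structures ahead of the existing list, for example heterogeneous Toeplitz, then heterogeneous AR(1) or heterogeneous compound symmetry. Allow an equal-variance structure only if none of these converges, and then report a small-sample-corrected robust standard error, stating which degrees of freedom go with it.

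Two further changes are matters of preference. Removing variance components would change little, since AIC never chose it in the simulations. Whether to choose by AIC or by first-to-converge among the heterogeneous structures is also open, provided it is fixed in advance.

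The cost is a sentence in each document and a different covariance option in the SAS code, with no effect on data, patients or timeline. If only the SAP is changed, its section 4, which now reports no change to the planned analysis, should record it.

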7.3.5 Pharmacokinetic analyses

Not applicable

7.4 INTERIM ANALYSES

No interim analysis is planned for this study.

7.5 HANDLING OF MISSING DATA

As defined for the MMRM, missing data are handled implicitly by the statistical model, rather than by using any imputation (see Section 7.3.2). In case of ANCOVA analyses, missing data will be imputed using the LOCF approach. If no value after first intake of trial medication is available, the baseline value will be used for HbA1c. Further details will be provided in the TSAP.

With respect to safety evaluations, it is not planned to impute missing values.

7.6 RANDOMISATION

The trial will be performed as a double-blind design with respect to the two active dose groups of empagliflozin. Eligible patients assessed by investigator will be randomised in blocks to the two study treatments in a 1:1 ratio. The randomisation will be stratified by the following factors:

- Pre-randomisation HbA1c value (<8.0%, ≥8.0%) using the Visit 1 HbA1c values for patients pre-treated with liraglutide alone and Visit 6 HbA1c values for other patients
- Pre-randomisation eGFR value (≥90 mL/min/1.73m², 60 to <90 mL/min/1.73m², 45 to <60 mL/min/1.73m²) calculated based on Visit 6 creatinine values.

The randomisation of patients to the treatment groups will be performed via an IRT. BI will arrange for the randomisation as well as packaging and labelling of trial medication. The randomisation list will be generated using a validated system, which involves a pseudorandom number generator and a supplied seed number so that the resulting allocation of medication numbers to treatment is both reproducible and non-predictable. The access to the randomisation codes will be controlled and documented.

7.7 DETERMINATION OF SAMPLE SIZE

The draft version of Japanese guideline 'Clinical Evaluation Guidelines for Antihyperglycemic Drugs' [R15-2907] requires one year long-term study on background therapies with several approved antidiabetic drugs. The guideline requires observing 50 to 100 patients during one year for each background therapy. The sample size for this trial was determined according to the outcome of the PMDA consultation on December 2014. At least 50 patients as 52-week completers including two doses were necessary for the background therapy with GLP-1 RA for safety evaluation.

Based on the above, and allowing for a discontinuation/dropout rate of approximately 20% during the trial, the sample size for empagliflozin 10 mg and 25 mg were determined at 32 per arm in the GLP-1 RA background group.

